9. After completing the analyses and entering his/her own data, the 2nd reader also combines his/her results with the results of the 1st reader in customized RET Fusion Excel Table and transfers all materials to the Reviewer.
11. Upon receiving the results, the reviewer:
 - a. Checks the slide and images against the final result of the Reader(s).
 - b. If the reviewer agrees with the 1st reader (when only one reader was involved) or with the combined score when two readers were involved, he/she places a “R” in the summary table next to the selected data for reporting.
 - c. If the Reviewer observations support a different conclusion from the results of the Reader(s), then the Reviewer performs independent analysis following the same guidelines as described above and submits the results to the director. In addition to entering his/her own data, the reviewer also enters the combination of readings (reviewer+1st reader or reviewer+2nd reader) that best represent the specimen.
12. When the reviewer scores the slide due to disagreement with the reader(s), the director takes the role of the reviewer and determines which results are considered are to be reported, placing a “R” in the Summary Table.
13. If the reviewer (or the director) agrees with the results from the Reader(s) but does not agree with representative images taken by the Reader(s), he/she must capture more representative images.
14. For documentation, reviewer (or director) selects the 2 best images per specimen and export them (as TIFF files) to the proper archival folders.
15. Reviewer drafts the report for each specimen and submits to the director.
16. For test specimens that do not pass QA, reviewer determines how new attempt should be run.

D. Instructions for Interpretation

Negative for RET rearrangement	Positive for KIF5B-RET fusion	Positive for RET rearrangement	Inconclusive
Signal: fused Red (R) and Green (G) with a separated Yellow (Y) Specimen: <20% of cells show fusion R/Y and single G Green	Signal: split Red and Green, with Red and Yellow fusion Specimen: ≥20% of cells show fusion R/Y and single G	Signal: split Red and Green, without Red and Yellow fusion Specimen: ≥20% of cells show split R and G but no fusion R/Y	Signal: Fused RGY, Separated R-G-Y, Separated R-G with fused GY, single R, single G Specimen: ≥50% of cells show inconclusive signals as major pattern

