FGFR1 gene copy number by silver in situ hybridization (SISH): SISH offers potential advantages over FISH for measurement of CNG in terms of rapidity, widespread applicability to diverse pathology laboratories and, potentially, cost savings as a screening assay. The measurement is assessed with bright light microscopy and preserves cell morphology. Thus, malignant cells and benign cells can be distinguished, and the long-term stability of the detection product permits repeated viewing of the slides. In our preliminary studies, we have merged polysomy (>4 distinct signals or dots per nucleus) and true amplification (obvious clusters of multiple signals or dots). As the clinical trial progresses, we will interrogate clinical response to ponatinib with FGFR1 polysomy or amplification to determine if amplification is the superior biomarker relative to increased polysomy.

In preliminary studies, we measured FGFR1 gene copy number with SISH and FISH assay on the lung cancer cell line TMA. Firstly, the SISH assay measurements closely agree with the determination of gene copy number by QPCR (Table 7). Moreover, SISH and FISH measurements were highly correlated ($p=0.68$, $p<0.0001$) and importantly, SISH was better able to discriminate the cell lines sensitive vs. resistant to ponatinib (ROC AUC 0.79, $p=0.033$ for SISH vs. 0.70, $p=0.15$ for FISH). Using the FGFR1 SISH assay, 59 early stage NSCLC patients (32 squamous, 22 adenocarcinoma and 5 NOS histologies) from a Polish lung tumor cohort have been analyzed. Overall, out of 57 evaluable cases (including 31 squamous cancers), 15 with copy number greater than 3 (5 with copy number >4) and 5 cases with FGFR1:CH8 ratios >2 were identified. With the exception of 3 cases that had FGFR1 copy number of 4, all cases with a copy number >4 and/or with an FGFR1:CH8 ratio >2 occurred in

squamous cancers. Thus, increased FGFR1 gene copy number gain is frequent in localized NSCLC, especially squamous cell carcinomas, a finding consistent with the published literature. The studies demonstrate that FGFR1 SISH is a clinically feasible assay going forward in the proposed studies.

We tested the FGFR1 ISH, IHC and SISH assays for their ability to identify the TKI sensitive cell lines within the lung cancer cell line TMA. Choosing an IC₅₀ cut point of ≤50nM to approximate clinically

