APPENDIX A: BIOMARKER PRESCREENING

A1. Sample capture flowsheet

*Internal cases to d/w PI re RET FISH as pan-negatives to be prioritized

FGFR1 SISH, ISH and RET FISH are described. See Lab Manual for detailed Standard Operating Procedures. Comparable information derived from other assays, e.g. NGS platforms for RET rearrangements, may be permissible as an entry criterion, following discussion with the PI. In such cases, attempts to confirm with the study specific assays should be made.

Material sufficient for some but not all assays will still be considered acceptable and assays will be prioritized in the following order: *FGFR1* SISH, *FGFR1* ISH, *RET* FISH.

For equivocal or inconclusive cases, confirmatory assays (e.g. RT-PCR for RET rearrangements) may be conducted and if a conclusive result is generated, may be permissible as an entry criterion, following discussion with the PI.

Excess unstained slides of the requested 20 x 4uM and/or tumor block will be archived and consenting will permit additional biomarker analyses to be conducted pertaining to the biology of lung cancer and/or outcomes from this study.

A2. FGFR1 Copy number and message levels ([name] lab):

I. Protocol for SISH Assay

FGFR1 gene copy number is to be detected using Silver in Situ Hybridization (SISH) on the Benchmark® XT automated stainer (Ventana Medical Systems, Inc.). One unstained slide of the adequate ID is to be stained for FGFR1 SISH, and another unstained slide is to be reserved as backup in case of assay failure.

FGFR1/ CH8 SISH Procedure

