Each FGFR1 mRNA ISH staining run is documented on the RNA ISH Procedure Checklist (See Associated Forms) for record keeping.

III. Specimen Evaluation and Scoring

FGFR1 SISH and FGFR1 mRNA ISH are evaluated and scored by the pathologist and an observer, following the criteria practiced at the [name] Biomarker Analysis Laboratory. When the difference between the two scores is greater than 20%, then the pathologist and the observer will jointly review the case and derive a consensus score. SISH scores are recorded on the SISH Scoring Sheet and mRNA ISH scores are recorded on the mRNA ISH Scoring Sheet (See Associated Forms). The final results are signed out the Lab Director. All score sheets are to be kept in the study binder for documentation.

A. SISH Scoring criteria:

Specimen evaluation is performed by a certified pathologist who assesses only the tumor tissue using a bright-field microscope, i.e. non-tumor, necrotic, degenerated, crushed, or clearly artifactual (edge, retraction, thermal) tissue is not evaluated. Examples of FGFR1 SISH are shown in figure 1. The pathologist scans the specimen using 400 or 600 X magnification and focuses on regions that appear to have the highest copy numbers and counts the black (gene) and red (centromere) signals in 50 non-overlapping nuclei in order to generate the gene copy number and the ratio between the gene copy number and centromere copy number on a continuous scale. A single copy of the gene is visualized as a single discrete black dot, whereas a tight cluster of black dots stacked so closely together that individual signals cannot be resolved, are considered amplified genes. Individual signals are given a score of one, and if clusters are present, the small clusters are counted as 6 and the large clusters are counted as 12. The same procedure is followed for scoring the red centromeric probe within the same nuclei for which black signals were counted. The gene copy number and ratio between the gene copy number and centromere copy number are averaged for the 50 nuclei that were evaluated and recorded. An FGFR1 copy number ≥ 4 is considered positive. The ratio to CH8 is not part of the initial criteria but will be assessed for its impact retrospectively.

[figure not shown]
[figure not shown]

Figure 1. Examples of FGFR 1 SISH. The scoring of FGFR1 and FGFR1:CH 8 ratio is: A 1.5, 0.8; B 1.9, 1.1; C 4.2, 1.4;

B. mRNA ISH Scoring criteria:

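### Joint review of the two SISH reads is triggered by a difference above 20%, not by reads on opposite sides of the ≥4 copy cutpoint that assigns the cohort

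*Combined protocol and SAP*

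**What the plan says.** Appendix A2, part III (Specimen Evaluation and Scoring) sets up a double read: "FGFR1 SISH and FGFR1 mRNA ISH are evaluated and scored by the pathologist and an observer". Under the SISH scoring criteria the pathologist "counts the black (gene) and red (centromere) signals in 50 non-overlapping nuclei", and the copy number is the average over those nuclei, on a continuous scale. The class is then binary: "An FGFR1 copy number ≥ 4 is considered positive". A joint review ending in a consensus score has one stated trigger: "When the difference between the two scores is greater than 20%, then the pathologist and the observer will jointly review the case". After that, "The final results are signed out the Lab Director".

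The opening part of Appendix A adds two general provisions. One is "For equivocal or inconclusive cases, confirmatory assays (e.g. RT-PCR for RET rearrangements) may be conducted", with use as an entry criterion subject to discussion with the principal investigator. The other is "See Lab Manual for detailed Standard Operating Procedures"; that manual is not among the documents.

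Section 5.2.2 sorts patients into four FGFR1 groups by SISH and ISH class. For RET FISH, Appendix A3 (Analysis and Scoring) works differently: the reviewer scores the slide independently when his or her observations point to a different conclusion from the reader's.

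**The concern.** The trigger measures how far apart two numbers are, but the trial uses only which side of 4 they fall on. A pair just either side of 4 is the case in which a second look can change the cohort, and it is also the case in which the difference tends to be small.

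SISH class feeds both primary objectives: biomarker prevalence in Part A, and the cohort in which a patient's response is counted in Part B. A changed class moves a patient between SISH+ISH+ and SISH−ISH+, or between SISH+ISH− and the double negative comparator. Cohorts have 12 evaluable patients and are judged on 3 responses, so single patients carry weight.

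The neighbourhood of the cutpoint is not empty. Of 57 evaluable tumors in the early-stage series of Section 3.1, "15 with copy number greater than 3 (5 with copy number >4") were found, so 15 − 5 = 10 (18%) lay above 3 and up to 4. The same paragraph mentions three cases with a copy number of 4.

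**Working it through.** **1. The plan's own figures.** With 12 patients and success at 3 or more responses, the exact binomial gives type I error 1 − P(X ≤ 2 | 0.05) = 1 − 0.9804 = 0.0196 and power 1 − P(X ≤ 2 | 0.40) = 1 − 0.0834 = 0.9166. Both agree with Section 10.3 (0.02; over 90%). Applying SISH ≥ 4 to Table 7 against IC50 ≤ 50 nM gives 4 true positives, 2 false positives, 3 false negatives and 12 true negatives. PPV is 4/6 = 67% and NPV 12/15 = 80%, as stated in Section 3.1.

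**2. Which discordant pairs escape.** Call the lower read l and the higher read h. The pair is discordant if l < 4 ≤ h, and is not reviewed if (h − l)/B ≤ 0.20. The base B is undefined, so three are shown.

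| l / h | B = l | B = mean | B = h | Reviewed? |
|---|---|---|---|---|
| 3.8 / 4.2 | 10.5% | 10.0% | 9.5% | no |
| 3.6 / 4.2 | 16.7% | 15.4% | 14.3% | no |
| 3.4 / 4.0 | 17.6% | 16.2% | 15.0% | no |
| 3.3 / 4.0 | 21.2% | 19.2% | 17.5% | depends on base |
| 3.4 / 4.2 | 23.5% | 21.1% | 19.0% | depends on base |
| 3.3 / 4.3 | 30.3% | 26.3% | 23.3% | yes |

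With B = l an escaping pair needs h ≤ 1.2 l, so l ≥ 4/1.2 = 3.33 and h < 1.2 × 4 = 4.8. With B = h it needs l ≥ 0.8 h, so l ≥ 3.2 and h < 4/0.8 = 5. The gap is confined to reads between about 3.2 and 5.

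**3. Share of discordant pairs that escape.** This needs the per-reader CV, which the documents do not give, so a range is assumed. Each read was simulated as true value × lognormal error, with true values uniform on 1–8 and 2 million specimens. Ranges run over the three bases.

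| Assumed CV | Discordant pairs not reviewed |
|---|---|
| 5% | 96–99% |
| 7% | 82–92% |
| 10% | 57–71% |
| 12% | 44–58% |
| 15% | 31–42% |
| 20% | 19–27% |
| 30% | 9–13% |

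A lognormal spread of true values (median 2.5) agrees within about 1 point. With the true value exactly 4, the share is 64–78% at CV 10% and 37–50% at CV 15%. As a reference point, pure Poisson counting of 50 nuclei gives CV = √(4/50)/4 = 7% at 4 copies and 81–92% unreviewed. Reader choice of fields and the scoring of clusters could raise that CV.

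**4. Share of all specimens.** A larger CV produces more discordant pairs but catches more of them. On the mean base with the uniform spread, (discordant) × (unreviewed) is 3.2% × 0.98 = 3.1% at CV 5%, 6.5% × 0.64 = 4.1% at 10%, 9.7% × 0.36 = 3.5% at 15% and 13.1% × 0.22 = 2.9% at 20%. These figures rest on the assumed spread. They count unreviewed disagreements, not misassigned patients.

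**5. ISH.** The cutpoint is 3+ on a 0–4+ scale. Reads of 2+ and 3+ differ by 1/3 = 33%, 1/2.5 = 40% or 1/2 = 50%, or by 1/4 = 25% of the scale range. All exceed 20%. Only division by five categories gives exactly 20% and no trigger.

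**6. Illustrative consequence.** Suppose misassigned patients respond at 5% and the rest at 40%. Power in a 12-patient cohort is then 0.917 with none misassigned, 0.886 with one, 0.845 with two and 0.792 with three.

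**The case against.** The strongest reply is that the gap may be small and already covered. The Lab Director signs out every result. The SISH criteria describe the pathologist's own count, which is a natural score of record. Confirmatory assays are allowed for equivocal cases, and the unseen Lab Manual may contain a rule. This stands to the extent that a reader might infer such pairs are left unresolved, and the documents do not show that. They show only that Appendix A states no rule. Sign-out does not say which read prevails, confirmatory testing is optional, and equivocal is not defined for SISH.

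Other inferences go too far:

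- **That discordant pairs usually escape review.** This holds only if the per-reader CV is below roughly 11–13%; above that, most are caught.
- **That the check is off wherever it matters.** Wide straddles such as 3.3 and 4.3 are reviewed on any base. Review of clearly positive pairs is also useful, because Section 10.3 plans exploratory analyses of higher SISH cutpoints.
- **That 18% of tumors are at risk of discordance.** The 10 of 57 covers everything above 3 up to 4, and many of those may lie well below the cutpoint. The series was early-stage, whereas the trial screens advanced disease.
- **That cohort verdicts will change.** The documents do not support an expected number of misassigned patients, and a 5% versus 40% contrast is severe for tumors close to one cutpoint derived from 21 cell lines.

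**Conclusion.** The point holds, for SISH only. Under the rule as written, two reads that disagree on positivity but differ by 20% or less trigger no consensus. Appendix A does not name the score that then assigns the cohort, and the undefined base makes pairs such as 3.4 and 4.2 ambiguous. This much follows from the text without any assumption.

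The size is conditional on reader variability: from nearly all discordant pairs unreviewed at a 5% CV to about a fifth or a quarter at 20%. That rests on two independent readers with proportional error. The plan's sample size, type I error and power are correct as stated and are unaffected. It is an inexpensive improvement to a rule behind both primary objectives, not an error that undermines the design.

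**What to change.** In Appendix A2, part III, and the Lab Manual:

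- Keep the trigger at a difference above 20% and define its base, for example the mean of the two reads.
- Add joint review and consensus whenever the two SISH reads disagree on positive or negative status at ≥4 copies. This follows the conclusion-based adjudication that Appendix A3 already uses for RET FISH.
- State that the consensus score, or the mean of two concordant reads, is the score used for cohort assignment and prevalence. The mean of two reads on the same side of 4 stays on that side, so this creates no new reclassification.

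The cost is a few sentences and some extra joint reviews by the same two readers. No existing review is dropped, so there is no offsetting saving. Score sheets are kept in the study binder, so discordant pairs already read can be identified.

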APPENDIX B: ECOG AND KARNOFSKY PERFORMANCE STATUS

ECOG Performance Status Scale		Karnofsky Performance Scale	
Grade	Descriptions	Percent	Description
0	Normal activity. Fully active, able to carry on all pre-disease performance without restriction.	100	Normal, no complaints, no evidence of disease.
		90	Able to carry on normal activity; minor signs or symptoms of disease.
1	Symptoms, but ambulatory. Restricted in physically strenuous activity, but ambulatory and able to carry out work of a light or sedentary nature (e.g., light housework, office work).	80	Normal activity with effort; some signs or symptoms of disease.
		70	Cares for self, unable to carry on normal activity or to do active work.
2	In bed <50% of the time. Ambulatory and capable of all self-care, but unable to carry out any work activities. Up and about more than 50% of waking hours.	60	Requires occasional assistance, but is able to care for most of his/her needs.
		50	Requires considerable assistance and frequent medical care.
3	In bed >50% of the time. Capable of only limited self-care, confined to bed or chair more than 50% of waking hours.	40	Disabled, requires special care and assistance.
		30	Severely disabled, hospitalization indicated. Death not imminent.
4	100% bedridden. Completely disabled. Cannot carry on any self-care. Totally confined to bed or chair.	20	Very sick, hospitalization indicated. Death not imminent.
		10	Moribund, fatal processes progressing rapidly.
5	Dead.	0	Dead.

APPENDIX C: BLOOD SAMPLE PREPARATION FOR PG AND BANKED PLASMA, BLOOD BASED EFFICACY/PROGNOSIS/SAFETY BIOMARKERS

Plasma and buffy coat collection.

Plasma collection kits will be provided by the Biorepository Core Facility, all components of the collection kits will be barcoded to enable easy identification and tracking. Kits contain a vacutainer for blood collection, instructions, and form for specimen annotation and tracking. Patients will have 10mL of blood collected in heparinized tubes. After collection the kits will be transferred to the Biorepository Core facility for processing and storage. Plasma will be separated by centrifugation. The resultant plasma will be stored at -80°C in 0.5 mL aliquots in barcoded screw-cap polypropylene cryogenic tubes. Buffy coat will be stored at -80°C as a source of genomic DNA. DNA from buffy coat will be isolated using Qiagen isolation kits on the QIAcube instrument, and stored in aliquots in barcoded screw-cap polypropylene cryogenic tubes at -80°C.

Laboratory PD Measurements

Plasma FGF23, intact parathyroid hormone levels, serum and urine phosphorus, serum calcium and serum and urine creatinine will be measured at the University Hospital laboratories.

Fibroblast growth factor-23 will be measured in plasma EDTA using a commercially available ELISA that measures the full-length peptide (Kainos Laboratories, Japan). We have prior experience using this assay in large-scale epidemiologic studies. In our hands, the intra-assay CV was 5% and the inter-assay CV was 9.9%. There is no effect of 3 freeze-thaw cycles on the amount of analyte detected.

Intact parathyroid hormone will be measured in EDTA plasma on a Roche Elecsys 2101 Analyzer using a sandwich immunoassay method (Roche Diagnostics, Indianapolis). In the first incubation, the patient sample reacts with a biotinylated monoclonal PTH-specific antibody and a monoclonal PTH-specific antibody labeled with a ruthenium complex to form a sandwich complex. During the second incubation, streptavidin-coated microparticles are added and the complex becomes bound to the solid phase via interaction of biotin and streptavidin. The microparticles are then captured magnetically and unbound substance is removed. Application of a voltage to the electrode then induces chemiluminescent emission that is measured by a photomultiplier. The amount of light produced is directly proportional to the amount of PTH in the sample. The Roche reported CV is 6.5% at a concentration of 26.7 pg/mL, 3.9% at a concentration of 52.5 pg/mL, and 3.0% at a concentration of 261pg/mL. Intact parathyroid hormone will be measured as it may also have an effect of urine phosphate excretion.

Serum and urine phosphorus will be measured using a timed-rate colorimetric reaction with ammonium molybdate at acidic pH clinical analyzer (Roche Modular P Chemistry Analyzer), which has continued surveillance for accuracy and drift as the same system is used for clinical analysis. Both analytes have inter-assay CVs < 3%. Once serum and urine phosphorus measurements are completed, they will be combined with serum and urine creatinine, which will be measured by standard, and CLIA certified clinical assays to calculate the urinary fractional excretion of phosphorus (FePi) using the following equation (each measurement in mg/dL):

$$\text{FePi (\%)} = (\text{Urine Phosphorus} * \text{Serum Creatinine} * 100) / (\text{Serum Phosphorus} * \text{Urine Creatinine})$$

Serum Calcium will be measured using indirect potentiometry with a Ca^{2+} ion selective electrode on a Beckman DxC Synchron clinical analyzer. The normal reference range is 8.9-10.2 mg/dL and the analytical measurement range is 2.0-20.0 mg/dL. The interassay CV is <1.7% at 9.5 mg/dL.

APPENDIX D: CTCAE V. 4.0

A searchable database of adverse event terms may be found at:

<http://safetyprofiler-ctep.nci.nih.gov/CTC/CTC.aspx>

APPENDIX E: RECIST V. 1.1

Highlights below. See following reference for full details:

At baseline, tumour lesions/lymph nodes will be categorised measurable or non-measurable as follows:

Measurable Tumour Lesions: Must be accurately measured in at least one dimension (longest diameter in the plane of measurement is to be recorded) with a minimum size of:

- 10 mm by CT scan (CT scan slice thickness no greater than 5 mm; see Appendix II on imaging guidance).
- 10 mm caliper measurement by clinical exam (lesions which cannot be accurately measured with calipers should be recorded as non-measurable).
- 20 mm by chest X-ray.

Malignant lymph nodes: To be considered pathologically enlarged and measurable, a lymph node must be ≥ 15 mm in short axis when assessed by CT scan (CT scan slice thickness recommended to be no greater than 5 mm). At baseline and in follow-up, only the short axis will be measured and followed (see Schwartz et al. in this Special Issue¹⁵). See also notes below on 'Baseline documentation of target and non-target lesions' for information on lymph node measurement.

Non-measurable:

All other lesions, including small lesions (longest diameter < 10 mm or pathological lymph nodes with ≥ 10 to < 15 mm short axis) as well as truly non-measurable lesions. Lesions considered truly non-measurable include: leptomeningeal disease, ascites, pleural or pericardial effusion, inflammatory breast disease, lymphangitic involvement of skin or lung, abdominal masses/abdominal organomegaly identified by physical exam that is not measurable by reproducible imaging techniques.

Special considerations regarding lesion measurability

Bone lesions, cystic lesions, and lesions previously treated with local therapy require particular comment:

Bone lesions:

- Bone scan, PET scan or plain films are not considered adequate imaging techniques to measure bone lesions. However, these techniques can be used to confirm the presence or disappearance of bone lesions.
- Lytic bone lesions or mixed lytic-blastic lesions, with identifiable soft tissue components, that can be evaluated by cross sectional imaging techniques such as CT or MRI can be considered as measurable lesions if the soft tissue component meets the definition of measurability described above.
- Blastic bone lesions are non-measurable.

Cystic lesions:

- Lesions that meet the criteria for radiographically defined simple cysts should not be considered as malignant lesions (neither measurable nor non-measurable) since they are, by definition, simple cysts.
- ‘Cystic lesions’ thought to represent cystic metastases can be considered as measurable lesions, if they meet the definition of measurability described above. However, if non-cystic lesions are present in the same patient, these are preferred for selection as target lesions.

Lesions with prior local treatment:

- Tumour lesions situated in a previously irradiated area, or in an area subjected to other loco-regional therapy, are usually not considered measurable unless there has been demonstrated progression in the lesion. Study protocols should detail the conditions under which such lesions would be considered measurable.

Specifications by methods of measurements

All measurements should be recorded in metric notation, using calipers if clinically assessed. All baseline evaluations should be performed as close as possible to the treatment start and never more than 4 weeks before the beginning of the treatment.

Method of assessment

The same method of assessment and the same technique should be used to characterise each identified and reported lesion at baseline and during follow-up. Imaging based evaluation should always be done rather than clinical examination unless the lesion(s) being followed cannot be imaged but are assessable by clinical exam.

Clinical lesions: Clinical lesions will only be considered measurable when they are superficial and ≥ 10 mm diameter as assessed using calipers (e.g. skin nodules). For the case of skin lesions, documentation by colour photography including a ruler to estimate the size of the lesion is suggested. As noted above, when lesions can be evaluated by both clinical exam and imaging, imaging evaluation should be undertaken since it is more objective and may also be reviewed at the end of the study.

Chest X-ray: Chest CT is preferred over chest X-ray, particularly when progression is an important endpoint, since CT is more sensitive than X-ray, particularly in identifying new lesions. However, lesions on chest X-ray may be considered measurable if they are clearly defined and surrounded by aerated lung.

CT, MRI: CT is the best currently available and reproducible method to measure lesions selected for response assessment. This guideline has defined measurability of lesions on CT scan based on the assumption that CT slice thickness is 5 mm or less. When CT scans have slice thickness greater than 5 mm, the minimum size for a measurable lesion should be twice the slice thickness. MRI is also acceptable in certain situations (e.g. for body scans).

Ultrasound: Ultrasound is not useful in assessment of lesion size and should not be used as a method of measurement. Ultrasound examinations cannot be reproduced in their entirety for independent review at a later date and, because they are operator dependent, it cannot be guaranteed that the same technique and measurements will be taken from one assessment to the next. If new lesions are identified by ultrasound in the course of the study, confirmation by CT or MRI is advised. If there is concern about radiation exposure at CT, MRI may be used instead of CT in selected instances.

Endoscopy, laparoscopy: The utilisation of these techniques for objective tumour evaluation is not advised. However, they can be useful to confirm complete pathological response when biopsies are obtained or to determine relapse in trials where recurrence following complete response or surgical resection is an endpoint.

Tumour markers: Tumour markers alone cannot be used to assess objective tumour response. If markers are initially above the upper normal limit, however, they must normalise for a patient to be considered in complete response. Because tumour markers are disease specific, instructions for their measurement should be incorporated into protocols on a disease specific basis.

Cytology, histology: These techniques can be used to differentiate between PR and CR in rare cases if required by protocol (for example, residual lesions in tumour types such as germ cell tumours, where known residual benign tumours can remain). When effusions are known to be a potential adverse effect of treatment (e.g. with certain taxane compounds or angiogenesis inhibitors), the cytological confirmation of the neoplastic origin of any effusion that appears or worsens during treatment can be considered if the measurable tumour has met criteria for response or stable disease in order to differentiate between response (or stable disease) and progressive disease.

Tumour response evaluation

Assessment of overall tumour burden and measurable disease

To assess objective response or future progression, it is necessary to estimate the overall tumour burden at baseline and use this as a comparator for subsequent measurements. Only patients with measurable disease at baseline should be included in protocols where objective tumour response is the primary endpoint. Measurable disease is defined by the presence of at least one measurable lesion. In studies where the primary endpoint is tumour progression (either time to progression or proportion with progression at a fixed date), the protocol must specify if entry is restricted to those with measurable disease or whether patients having non-measurable disease only are also eligible.

Baseline documentation of ‘target’ and ‘non-target’ lesions

When more than one measurable lesion is present at baseline all lesions up to a maximum of five lesions total (and a maximum of two lesions per organ) representative of all involved organs should be identified as target lesions and will be recorded and measured at baseline (this means in instances where patients have only one or two organ sites involved a maximum of two and four lesions respectively will be recorded).

Target lesions should be selected on the basis of their size (lesions with the longest diameter), be representative of all involved organs, but in addition should be those that lend themselves to reproducible repeated measurements. It may be the case that, on occasion, the largest lesion does not lend itself to reproducible measurement in which circumstance the next largest lesion which can be measured reproducibly should be selected.

Lymph nodes merit special mention since they are normal anatomical structures which may be visible by imaging even if not involved by tumour. Pathological nodes which are defined as measurable and may be identified as target lesions must meet the criterion of a short axis of ≥ 15 mm by CT scan. Only the short axis of these nodes will contribute to the baseline sum. The short axis of the node is the

diameter normally used by radiologists to judge if a node is involved by solid tumour. Nodal size is normally reported as two dimensions in the plane in which the image is obtained (for CT scan this is almost always the axial plane; for MRI the plane of acquisition may be axial, saggital or coronal). The smaller of these measures is the short axis. For example, an abdominal node which is reported as being 20 mm × 30 mm has a short axis of 20 mm and qualifies as a malignant, measurable node. In this example, 20 mm should be recorded as the node measurement. All other pathological nodes (those with short axis ≥ 10 mm but < 15 mm) should be considered non-target lesions. Nodes that have a short axis < 10 mm are considered non-pathological and should not be recorded or followed.

A sum of the diameters (longest for non-nodal lesions, short axis for nodal lesions) for all target lesions will be calculated and reported as the baseline sum of diameters. If lymph nodes are to be included in the sum, then as noted above, only the short axis is added into the sum. The baseline sum diameters will be used as reference to further characterise any objective tumour regression in the measurable dimension of the disease.

All other lesions (or sites of disease) including pathological lymph nodes should be identified as non-target lesions and should also be recorded at baseline. Measurements are not required and these lesions should be followed as ‘present’, ‘absent’, or in rare cases ‘unequivocal progression’ (more details to follow). In addition, it is possible to record multiple non-target lesions involving the same organ as a single item on the case record form (e.g. ‘multiple enlarged pelvic lymph nodes’ or ‘multiple liver metastases’).

Response criteria

This section provides the definitions of the criteria used to determine objective tumour response for target lesions.

Evaluation of target lesions

Complete Response (CR):

Disappearance of all target lesions. Any pathological lymph nodes (whether target or non-target) must have reduction in short axis to < 10 mm.

Partial Response (PR):

At least a 30% decrease in the sum of diameters of target lesions, taking as reference the baseline sum diameters.

Progressive Disease (PD):

At least a 20% increase in the sum of diameters of target lesions, taking as reference the smallest sum on study (this includes the baseline sum if that is the smallest on study). In addition to the relative increase of 20%, the sum must also demonstrate an absolute increase of at least 5 mm. (Note: the appearance of one or more new lesions is also considered progression).

Stable Disease (SD):

Neither sufficient shrinkage to qualify for PR nor sufficient increase to qualify for PD, taking as reference the smallest sum diameters while on study.

